4.3 Follow-up Analysis

The follow-up analysis is planned at the end of the trial after all patients complete the 30-day follow-up period or terminate early from the study during the follow-up period. The follow-up analysis will focus on the open-label treatment period. For the open-label treatment period,

1. Only descriptive summaries will be provided and no statistical modeling or statistical hypothesis tests will be performed.
2. Neither sensitivity nor supplementary analysis will be performed.
3. Analysis results will be presented by the treatment patients received during the double-masked treatment period.

Efficacy analyses are based on data collected from open-label treatment period. Safety analyses are based on data collected from open-label treatment period as well as 30-day follow-up data that are not included in the primary analysis.

5 General Statistical Considerations

The primary efficacy endpoint will be tested at the level of significance of 0.05 two-sided. Other efficacy endpoints will be tested in a sequential order as listed in Section 3.2.2 only when statistical significance is achieved for the primary efficacy endpoint and the other preceding endpoint in the prespecified order is statistically significant at the 0.05 significant level (two-sided).

In general, continuous data will be summarized by treatment group using descriptive statistics (number, mean, standard deviation (SD), minimum, 25th (Q1) percentile, median, 75th (Q3) percentile, and maximum). Categorical data will be summarized by treatment group using frequency tables (frequencies and percentages). SD will be presented to two decimal places beyond the precision with which the data was captured. Mean, median, Q1, and Q3 will be presented to one decimal places beyond the precision with which the data was captured. Minimum and maximum will be presented to the precision with which the data was captured. When count data are presented, the percentage will be suppressed when the count is zero in order to draw attention to the non-zero counts. A row denoted “Missing” will be included in count tabulations where specified on the shells to account for dropouts and missing values. The denominator for all percentages will be the number of patients (including the missing category) in that treatment group within the analysis set of interest, unless otherwise specified. P-values will be rounded to 4 decimal places. If a p-value is less than 0.0001 it will be reported as “<0.0001.” If a p-value is greater than 0.9999 it will be reported as “>0.9999”.

All study-related raw data that support the corresponding tables and figures will be presented in data listings. Unless otherwise noted, all data listings will be sorted by treatment group and patient number.

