3.1 Overall Study Design and Plan

This is a randomized, double-masked, placebo-controlled, parallel-group, multicenter trial. Patients will be screened for the trial within 4 weeks prior to the Baseline (Day 1) Visit. Approximately 57 patients who meet the trial eligibility criteria will be randomized on Day 1 in a 2:1 ratio to receive 8 infusions of TEPEZZA (10 mg/kg for the first infusion and 20 mg/kg for the remaining 7 infusions) or placebo once every 3 weeks (q3W). All patients will enter a 24-week double-masked treatment period, during which trial drug will be infused on Day 1 (Baseline) and Weeks 3, 6, 9, 12, 15, 18 and 21 (with a final visit at Week 24 of the 24-week treatment period).

At the end of the double-masked treatment period (Week 24), all patients will be assessed for treatment response. The primary treatment response is assessed based on the change in proptosis from Baseline. Proptosis responders were defined as patients with a 2 mm or greater reduction in proptosis from Baseline in the study eye, without deterioration (i.e., 2 mm or greater increase) of proptosis in the fellow eye. Proptosis non-responders who have completed the double-masked treatment period may choose to receive 8 infusions of TEPEZZA (10 mg/kg for the first infusion and 20 mg/kg for the remaining 7 infusions) in an open-label fashion q3W at Weeks 24, 27, 30, 33, 36, 39, 42 and 45. These patients will return to the clinic at Week 48 for End-of-Treatment assessments, and patients will be contacted by phone/email 30 days after the Week 48 Visit for safety assessment. Proptosis responders, as well as non-responders who choose not to receive TEPEZZA in an open-label fashion, will enter a 30-day Follow-up Period, during which study drug will not be administered. These patients will be contacted by phone/email 30 days after the Week 24 Visit for safety assessment.

An overview of the trial design is presented in **Figure 1**, and details of trial activities are presented in Section 15.1, Schedule of Assessments.

Figure 1 Schematic of Trial Design

Screen	BL	Double-masked Treatment Period TEPEZZA or Placebo ^{1,2} 24 Weeks										Open-label Treatment Period ² (Proptosis Non-responders who Choose to Receive Open-label TEPEZZA)							30-day Follow- up Period ²					
		*	*	*	*	*	*	*	*	*	*	*	*	*	*	*	*	*	*	*	*	*	*	*
4 weeks predose	Day 1 ³	W3 ³	W6	W9	W12	W15	W18	W21	W24 ^{3,4,5}	W27 ³	W30	W33	W36	W39	W42	W45	W48 ³							

Randomization¹ <———— Trial Week —————>

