4.2 Primary Analysis

The primary analysis of efficacy, safety and tolerability is planned after all patients complete the Week 24 visit assessments in the double-masked treatment period or terminate early from the study prior to Week 24. Efficacy analyses are based on data collected from the Screening visit through Week 24 visit. Safety analyses are based on data collected up to last patient’s Week 24 visit date.

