10.1 Adverse Events

Adverse events will be coded using MedDRA version 24.0. AEs that occur during Screening and prior to dosing on Day 1 will be considered pre-treatment AEs. TEAEs for the double-masked treatment period is defined as AEs with onset date on or after the first dose of study drug during the double-masked treatment period prior to receiving the first dose of TEPEZZA during open-label treatment period for patients who entered open-label treatment period, or through 3 weeks (21 days) after the last dose of study drug during the double-masked treatment period for patients who did not enter open-label treatment period. TEAEs for open-label treatment period defined as AEs with onset date on or after first dose of TEPEZZA during the open-label treatment period through 3 weeks (21 days) after last dose of TEPEZZA during the open-label treatment period. All analyses for TEAEs will be split to TEAEs reported during the double-masked treatment period and open-label treatment period separately. The follow-up AE reporting period begins 3 weeks (21 days) after the last dose of study drug through completion of the follow-up period.

An overall summary of all TEAEs including the number and percentage of patients experiencing at least one occurrence of a TEAE, serious TEAEs, treatment-related TEAEs, treatment-related serious TEAEs, TEAEs resulting in study drug discontinuation, TEAEs of special interest, TEAEs leading to death along with the summary of National Cancer Institute Common Terminology Criteria for Adverse Events (NCI-CTCAE) grade 3 or higher will be provided.

Additionally, AEs and SAEs reported during the follow-up period after each treatment period will be presented by SOC and PT separately.

All AEs, AEs with CTCAE Grade 3 or higher, SAEs, AEs leading to discontinuation of study drug, AE of special interest, and deaths will be presented in separate by-subject listings.

Signs and symptoms associated with Infusion reaction and anaphylaxis will be recorded and included in a by-subject listing.

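### Read literally, SAP 4.2 and 4.3 divide 30-day follow-up AEs and SAEs between two analyses at a calendar date, and no table is said to pool the parts

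*SAP*

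**What the plan says.** SAP 4.2 sets one calendar cut-off for safety in the primary analysis: "Safety analyses are based on data collected up to last patient’s Week 24 visit date". The efficacy sentence before it refers to visits, from Screening through Week 24. The safety sentence refers to a date shared by all patients.

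SAP 4.3 describes a second analysis, "planned at the end of the trial after all patients complete the 30-day follow-up period or terminate early". Its safety data come in two parts. Open-label data are taken without restriction: "Safety analyses are based on data collected from open-label treatment period". Follow-up data carry a restriction: "as well as 30-day follow-up data that are not included in the primary analysis".

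SAP 10.1 defines follow-up AEs relative to each patient: "The follow-up AE reporting period begins 3 weeks (21 days) after the last dose of study drug through completion of the follow-up period". It then promises that "AEs and SAEs reported during the follow-up period after each treatment period will be presented by SOC and PT separately". It does not say whether those tables are cumulative over the two analyses. SAP 5 sets the default denominator for percentages as all patients in the treatment group within the analysis set, unless otherwise specified.

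**The concern.** Patients who reached Week 24 well before the last patient have some or all of their follow-up inside the primary analysis. The restriction in SAP 4.3 then removes those data from the end-of-trial analysis. The two follow-up tables become non-overlapping pieces. Which piece holds a patient's events depends on when that patient enrolled, while the default denominator remains the whole group.

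TEAE tables close 21 days after the last dose, at about Week 24 or Week 48, and the AESI summary in SAP 10.1.6 is limited to TEAEs. The follow-up tables are therefore the only ones that the SAP sets out specifically for events in the 30 days after treatment. With 38 and 19 patients planned, moving one or two events between tables visibly changes a percentage. A reader who takes the end-of-trial table as the final account would see too few post-treatment events.

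**Working it through.** The plan gives no figure for this split, so there is none to reproduce. The check puts the two data rules together and asks how much follow-up falls on each side of the cut.

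**Inputs from the documents.** The cut-off is the last patient's Week 24 visit date (SAP 4.2). Patients who do not enter open-label treatment have one safety contact 30 days after Week 24: "These patients will be contacted by phone/email 30 days after the Week 24 Visit for safety assessment" (SAP 3.1). Open-label entrants have theirs 30 days after Week 48, which is 168 + 30 = 198 days after their own Week 24.

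**Assumptions.** Accrual is uniform over E days, with E not stated in the documents. All visits are on schedule. The time from a patient's Week 24 to the cut-off is then uniform on 0 to E.

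**Two ways to apply the cut.** If events are cut by onset date and are uniform over follow-up, the relevant share is follow-up time. If they are cut by collection date, it is the share of 30-day contacts made before the cut-off.

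- After masked treatment, by time (E of at least 30): 1 − 15/E
- After masked treatment, by contact: 1 − 30/E
- After open-label treatment, by time: (E − 183)/E for E of at least 198; (E − 168)²/(60E) for E from 168 to 198; 0 below 168
- After open-label treatment, by contact: (E − 198)/E for E above 198; otherwise 0

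Examples at E = 365: 1 − 15/365 = 0.959; 1 − 30/365 = 0.918; (365 − 183)/365 = 0.499; (365 − 198)/365 = 0.458.

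Share of follow-up falling before the cut-off:

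| E (days) | After masked, by time | After masked, by contact | After open-label, by time | After open-label, by contact |
|---|---|---|---|---|
| 90 | 83% | 67% | 0% | 0% |
| 180 | 92% | 83% | 1% | 0% |
| 270 | 94% | 89% | 32% | 27% |
| 365 | 96% | 92% | 50% | 46% |
| 730 | 98% | 96% | 75% | 73% |

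If six months is taken as 182.5 days, the open-label figure by time is 2%. Open-label follow-up starts to fall before the cut only when E passes 168 days (24 weeks) by time, or 198 days (about 28 weeks) by contact.

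**Illustration.** Assume a true follow-up AE risk of 10%, no open-label entry, at most one event per patient, the contact rule and the default denominator. The primary table shows 10 × (1 − 30/E) percent and the end-of-trial table shows 10 × 30/E percent. That gives 8.3% and 1.7% at 180 days, 9.2% and 0.8% at 365 days, and 9.6% and 0.4% at 730 days.

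**The case against.** The strongest reply is that SAP 4.3 only describes data scope, whereas SAP 10.1 governs the tables. Its definition of the follow-up period runs to completion for each patient and has no calendar cut, so an end-of-trial table built to that definition would be complete. This does not settle the matter. A definition of the period does not cancel an explicit restriction on which data enter the analysis, and SAP 10.1 says nothing about pooling. The clause might instead have been meant to say that follow-up data are, by their nature, not part of the primary analysis. That conflicts with the calendar cut in SAP 4.2, which does not exclude earlier patients' follow-up. The text needs correcting on either reading.

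Several limits do stand:

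- No data are lost. The share missing from the end-of-trial table is the share reported in the primary table.
- Safety is descriptive, with no hypothesis tests (SAP 10).
- SAP 10.1 lists all AEs and SAEs by subject, so the full count can be rebuilt.
- The denominator is a default, and the table shells, which are not part of these documents, might change it.

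A reader might infer that the end-of-trial table after open-label treatment must understate events. The documents do not support that without an accrual length: below about 24 weeks it is complete. A reader might also infer that adding the two tables would seriously double-count patients. At 12 months' accrual only about 57 × 30/365 ≈ 5 patients would have follow-up straddling the cut if all 57 were non-entrants. One of them would also need the same term on both sides within 30 days.

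**Conclusion.** The point holds as a literal reading of SAP 4.2 and 4.3 together. For follow-up after masked treatment, the end-of-trial table would omit about 92%, 96% and 98% of follow-up time at 6, 12 and 24 months' accrual, or about 83%, 92% and 96% of contacts. The primary table would be short by the complement, 2% to 17%. For follow-up after open-label treatment, about 46% to 50% would be missing from the end-of-trial table at 12 months and 0% to 2% at 6 months. These figures rest on uniform accrual and on-schedule visits, and accrual length is assumed throughout.

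It would go too far to say that the safety record is incomplete or that the trial's main conclusions are at risk. Efficacy is untouched. Open-label TEAEs are unaffected because SAP 4.3 takes all open-label data. Masked TEAEs are essentially unaffected because their window closes at about Week 24. This is a correctable reporting rule for descriptive follow-up AE and SAE tables. It should be fixed because complete data are in hand when the end-of-trial analysis is run and the SAP gives no reason to leave part of them out.

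**What to change.** Replace the safety sentence in SAP 4.3 with: *Safety analyses are based on all data collected in the open-label treatment period and all 30-day follow-up data, for all patients, whether or not they were included in the primary analysis.*

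Keep the follow-up AE and SAE tables in the primary analysis, and label them as partial, with data cut at the last patient's Week 24 visit. They should not be dropped, because that would take known post-treatment AEs and SAEs out of the primary report.

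The cost is one sentence and a table label. The same tables are run on cumulative data, with no new data collection.

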5.1 Sample Size

A total of 57 patients (38 in the TEPEZZA group and 19 in the placebo group) will be enrolled in the trial to detect at least a 2-mm mean difference between the 2 treatment groups in the change from Baseline of proptosis values at Week 24 in order to have 81% power at the two-sided 0.05 level of significance. The sample size was determined assuming that the mean difference in

proptosis change between the 2 groups is at least 2.0 mm (clinically relevant) and the standard deviation of proptosis change values is 2.5 for both groups (larger than the observed in Phase 2 and Phase 3 active TED trials).

5.2 Randomization, Stratification, and Masking

Patients will be randomly assigned to receive TEPEZZA or placebo using a 2:1 allocation ratio on Day 1 of the double-masked treatment period. No stratification factors will be considered for patient randomization.

In the double-masked treatment period, the clinical trial will be performed in a double-masked manner, while the pharmacists or designees responsible for preparing the TEPEZZA or placebo solutions for IV administration will not be masked to the identity of the trial drug.

Pharmacists/designees will provide trial drug in infusion bags (fully diluted for administration) to site personnel with appropriate masked labels. The patient, Investigator, and all other site personnel will be masked to the treatment being administered.

In the double-masked treatment period, all investigative site staff directly involved in this trial, except for unmasked pharmacy personnel, will remain masked from Screening through analysis of the open-label treatment data and all site close-out visits. The Sponsor and its designees may be unmasked after the double-masked treatment period database lock.

5.3 Analysis Set

5.3.1 Intent-to-Treat (ITT)

The ITT analysis set is comprised of all patients who are randomized to receive study drug (either TEPEZZA or placebo). This will be the primary analysis set for efficacy analysis for each treatment period. Patients will be analyzed according to their randomized treatment assignment.

5.3.2 Modified Intent-to-Treat (mITT)

The modified intent-to-treat (mITT) analysis set will include all ITT patients who receive at least one dose of study drug and have at least one post-baseline measurement of the primary efficacy endpoint. The mITT analysis set will be used to perform a supplementary analysis of the primary efficacy analysis for the double-masked treatment period. Patients will be analyzed according to their randomized treatment assignment. If the ITT analysis set is the same as the mITT analysis set because all randomized patients have met the mITT definition, then analysis results based the mITT analysis set will not be provided.

5.3.3 Per Protocol (PP)

The per protocol (PP) analysis set includes all mITT patients who complete the double-masked treatment period and do not incur any major protocol violations that would challenge the validity of their data. The PP analysis set will also be used to conduct as a supplementary analysis of the primary efficacy analysis. Patients will be analyzed according to treatment received. Major protocol violations that challenge the validity of the data will be identified by a masked review

on a regular basis while the study is ongoing and the review for major protocol deviations will be completed prior to the Week 24 database lock for the primary analysis.

5.3.4 Safety

The safety analysis set will include all patients who receive at least one dose of study drug. This will be the primary analysis set for safety evaluation for each treatment period. Patients will be analyzed according to treatment received. In the event a patient receives more than one treatment, the patient will be summarized by the treatment received most frequently.

5.3.5 PK

The PK analysis set will include all patients who receive at least one dose of TEPEZZA and have at least one post-dose PK sample. All PK analyses will be performed on the PK analysis set for each treatment period.

5.4 Assessment Windows

5.4.1 Study Day and TEPEZZA Study Day

The following two definitions of study day will be used for analysis purposes.

- Study Day will be calculated relative to the first dose of study drug (TEPEZZA or Placebo) (Day 1). Study day will be used for all analysis involving study day calculation in either double-masked treatment period or open-label treatment period.
- TEPEZZA Study Day will be calculated relative to the first dose of TEPEZZA whether it occurs in the double-masked treatment period or open-label treatment period (TEPEZZA Day 1). TEPEZZA study day will be used to calculate study day in the open-label treatment period only.

When study day or TEPEZZA study day is used for display or in comparisons the following algorithm will be used:

- Study day (or TEPEZZA study day) = date of assessment - Day 1 (or TEPEZZA Day 1) +1, if date of assessment \geq Day 1 (or TEPEZZA Day 1).
- Study day (or TEPEZZA study day) = date of assessment - Day 1 (or TEPEZZA Day 1), if date of assessment $<$ Day 1 (or TEPEZZA Day 1).

Note that the day before Day 1 is Day -1 (for analysis, there is no Day 0 for study day).

5.4.2 Baseline and TEPEZZA Baseline

The following two definitions of Baseline will be used for analysis purposes:

- Baseline will be defined as the last observation before the first dose of study drug (TEPEZZA or Placebo). Baseline will be used for all applicable analyses during the double-masked treatment period.

- TEPEZZA Baseline will be defined as the last observation before the first dose of TEPEZZA whether it occurs in the double-masked treatment period or open-label treatment period. TEPEZZA Baseline will be used for applicable analyses during the open-label treatment period.

Change from Baseline (or TEPEZZA Baseline) is defined as the post-baseline value minus the Baseline (or TEPEZZA Baseline) value for the given assessment.

5.4.3 Visit Windows for Analysis

For analyses that present visit-based data, the variables will be summarized based on the scheduled visits with derived analysis visit windows, with the exception of PK data, anti-drug antibody (ADA)/neutralizing antibody (NAb) data, and **CCI** [REDACTED], which will be analyzed based on nominal visits. For the visits on and after the first dose date, the actual visit date will be mapped to the derived analysis visit windows based on the study day.

Visit windows have been constructed so that every observation (unscheduled visits included) collected can be allocated to the scheduled analysis visit for planned analyses. The actual assessment day will be mapped to the windows defined for each scheduled study visit with following rules.

For multiple non-missing continuous measurements:

- If more than 1 assessment falls within a visit window, the closest non-missing valid assessment to the scheduled day will be used in the analysis.
- If 2 non-missing assessment actual dates are equidistant from the target day, the later visit will be used in the analysis.
- If there is more than 1 record on the selected day and the time is not recorded, the average will be taken, unless otherwise specified.
- For retest values of laboratory data, the retest value (the last valid observation assessed on the same visit day) will be chosen.

For multiple non-missing categorical measurements:

- For Baseline, the last available record on or prior to the date of the first dose of study drug will be selected. If there are multiple records with the same time or no time recorded on the same day, the value with the lowest severity will be selected (e.g., normal will be selected over abnormal for hematology).
- For postbaseline visits, if there are multiple records with the same time or no time recorded on the same day, the value with the worst severity within the window will be selected (e.g., abnormal will be selected over normal for hematology).

The Analysis Visit Window for the primary endpoint (change of proptosis), other endpoints (**CCI** [REDACTED]) and exploratory endpoint (**CCI** [REDACTED]) is shown in **Table 1**. The details for the other analysis visit window rules will be included in the TLF shell document.

Table 1 Analysis Visit Windows for Primary Endpoint

Analysis Visit	Target Study Day of Visit	Analysis Visit Window
Baseline	1	Non-missing assessment on or before the first dosing date (randomization)
Week 3	22	Day 2 to 32
Week 6	43	Day 33 to 64
Week 12	85	Day 65 to 106
Week 18	127	Day 107 to 148
Week 24	169	Day 149 to 179*
Week 27	190	Day 180 to 200
Week 30	211	Day 201 to 232
Week 36	253	Day 233 to 274
Week 42	295	Day 275 to 316
Week 48	337	≥ Day 317

* For patients who did not enter the open-label treatment period, Week 24 analysis visit window is \geq Day 149.

Data from all assessments (scheduled and unscheduled), including multiple assessments, will be included in listings.

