#### 9.5.3.1.6 Follow-up of Adverse Events

Any ongoing trial drug-related AE, including a clinically significant laboratory test abnormality, will be followed until resolved or until the event stabilizes and the overall clinical outcome has been ascertained.

In the event of unexplained, treatment-emergent, clinically significant abnormal laboratory test results or clinically significant changes in laboratory test results, the tests should be repeated immediately and followed until the values have returned to within the reference range or to Baseline for that patient.

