10.2 Clinical Laboratory Evaluations

With the exception of urine pregnancy tests, a central laboratory will be used for all protocol-specified clinical laboratory parameters. Laboratory results reported in conventional units will be converted to International System of Units (SI) for all summaries and listings for consistent results presentation.

Safety laboratory including hematology, chemistry, thyroid function tests and HbA1c values and change from Baseline values will be summarized by visit and treatment group for each treatment period using descriptive statistics. For fasting glucose and HbA1c, means and 95% CI of the test results measured at each scheduled visit will be plotted.

The laboratory assessment will be categorized as low, normal or high based on normal ranges. Shift tables using categories of low, normal and high from Baseline (i.e., based on normal reference ranges) to each post-baseline visit will be generated by treatment group for each treatment period for hematology, chemistry parameters, thyroid function and HbA1c, respectively.

The laboratory assessment will be graded using the NCI-CTCAE (v4.03) grading scale, when available. A shift table for glucose by NCI-CTCAE grade and visit will be generated by treatment group. Another table with summary of incidence of \geq Grade 3 glucose will be provided.

For those patients who experienced hyperglycemia (per AE reporting), their safety laboratory assessment results during the double-masked treatment period will be examined and summarized using the similar manner described above.

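### SAP 5.4.3 never selects continuous laboratory values by worst result, so a Grade 3 or higher glucose can drop out of the by-visit grade shift table, and the records behind the incidence table are not stated

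*SAP*

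**What the plan says.** SAP 5.4.3 sets the scope of its selection rules: "For analyses that present visit-based data, the variables will be summarized based on the scheduled visits with derived analysis visit windows". Two sets of rules follow.

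- **Continuous data.** The main rule for several readings is this: "If more than 1 assessment falls within a visit window, the closest non-missing valid assessment to the scheduled day will be used in the analysis". Where two dates are equally distant, the later is used. Several untimed records on the chosen day are averaged. Laboratory repeats have their own rule: "For retest values of laboratory data, the retest value (the last valid observation assessed on the same visit day) will be chosen".
- **Categorical measurements after Baseline.** The condition is narrow: "For postbaseline visits, if there are multiple records with the same time or no time recorded on the same day". Only then does it apply that "the value with the worst severity within the window will be selected (e.g., abnormal will be selected over normal for hematology".

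Table 1 in that section gives windows for proptosis and some other endpoints. Laboratory windows are left to the TLF shells.

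SAP 10.2 plans two graded glucose outputs. The first is by visit: "A shift table for glucose by NCI-CTCAE grade and visit will be generated by treatment group". The second is a separate incidence table for Grade 3 or higher glucose. It is not described as by visit, and its source records are not named. It corresponds to safety endpoint 5 in SAP 3.2.4 and Protocol 9.6.1.4, which is worded for fasting glucose.

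Protocol 9.5.3.1.6 says what follows an unexplained, treatment-emergent, clinically significant laboratory abnormality or change: "the tests should be repeated immediately and followed until the values have returned to within the reference range or to Baseline for that patient".

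**The concern.** Nearest-day and retest rules suit means and mean changes, where one representative value per patient and visit is wanted. They do not suit a severity table, whose purpose is to show how bad things became. Glucose is measured on a continuous scale and graded afterwards. If selection comes first, the grade table shows the grade of the selected record, not the highest grade reached in the window.

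The retest rule needs most care because retests are not random. Under Protocol 9.5.3.1.6 an abnormal result prompts the repeat, so the value discarded is typically the one that caused concern.

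What is at stake is the laboratory-based picture of a known risk. Hyperglycemia is an AESI, and Grade 3 or higher fasting glucose is an endpoint in its own right, separate from investigator-reported events. With 38 and 19 patients, one displaced reading can change what the table shows.

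**Working it through.** **Inputs.** Arm sizes of 38 TEPEZZA and 19 placebo come from SAP 5.1. The selection rules are those of SAP 5.4.3. On-treatment chemistry is scheduled at Weeks 6, 12, 18 and 24 (Protocol 2.1 and 9.5.6.2). The documents give no rate of Grade 3 glucose, no rate of retesting and no laboratory windows. They state no figure for this point that could be reproduced.

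**Step 1: apply the rules to hypothetical readings.** The target is Day 85 (Week 12). The window is assumed to be Days 65 to 106, as in Table 1.

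| Case | Continuous rules keep | Categorical rule | Worst value |
|---|---|---|---|
| A. Day 85, timed: Grade 3, then retest Grade 2 | Grade 2 | silent (times differ) | Grade 3 |
| B. Unscheduled Grade 3 on Day 75; scheduled Grade 1 on Day 85 | Grade 1 (distance 0 against 10 days) | silent (days differ) | Grade 3 |
| C. Day 85, untimed: Grade 3 and Grade 2 | average of the values, or the retest | Grade 3 | Grade 3 |
| D. Day 85, timed: Grade 2, then retest Grade 3 | Grade 3 | silent (times differ) | Grade 3 |
| E. Scheduled Grade 3 on Day 85; repeat Grade 1 on Day 88 | Grade 3 (distance 0 against 3 days) | silent (days differ) | Grade 3 |

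The Grade 3 reading is lost in A and B if the continuous rules feed the grade table, and the categorical rule rescues neither. In C the two rule sets can give different answers for the same blood samples. D and E show that the outcome depends on order and timing.

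**Step 2: direction.** The retest rule keeps the later of two same-day values. If the first is abnormal and prompts the second, the usual loss is of the higher value, as in A. The nearest-day rule ignores the value: it loses the high reading in B and keeps it in E.

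**Step 3: off-schedule readings.** On the Table 1 windows, an extra glucose drawn at the Week 9, 15 or 21 infusion visit (Days 64, 106, 148) falls in the Week 6, 12 or 18 window (targets 43, 85, 127). It is 64 − 43 = 106 − 85 = 148 − 127 = 21 days off target. It therefore loses to any reading less than 21 days from the target.

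**Step 4: size per patient.** One patient lost is 1/38 = 2.6 percentage points on TEPEZZA or 1/19 = 5.3 on placebo.

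**Step 5: range, by assumption only.** Suppose the incidence table also used windowed records and each affected TEPEZZA patient had exactly one Grade 3 reading.

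- 1 affected patient: 1/38 = 2.6% becomes 0% if that reading is displaced.
- 2 affected: 2/38 = 5.3% becomes 1/38 = 2.6% if one is displaced, and 0% if both are.
- 4 affected: 4/38 = 10.5% becomes 3/38 = 7.9% if one is displaced, and 0% if all are.

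A patient with a second Grade 3 reading that survives in any window stays in the count, so persistent hyperglycemia would be affected less.

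**The case against.** Several points on the other side are fair.

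- **The incidence table may not use these rules.** They govern visit-based presentations, and the incidence table is not described as one. A reader might infer that endpoint 5 itself will be understated. The documents do not support that; they leave the source records open. What stands against the plan is the silence.
- **A grade is a category, and the SAP takes the worst category.** Its hematology example shows that intent. But the stated condition stops at same-day records with the same or no time, so cases A and B remain uncovered.
- **The rules do not all favour normal values.** A reader might infer that they systematically narrow the difference between arms. That is not shown. The nearest-day rule can act either way, and a later-day repeat of a high scheduled reading usually leaves the high reading in place. Only the retest rule has an expected direction, and it may seldom apply: a central laboratory is used, so same-day repeats may be few. Protocol 9.5.3.1.6 is also limited to unexplained findings, while raised glucose is a known effect of the drug (Protocol 9.4.6.3.2).
- **Nothing disappears from the report.** SAP 5.4.3 puts every assessment in the listings. SAP 10.1.6 tabulates reported hyperglycemia as an AESI, and Grade 3 or higher TEAEs are tabulated as well. Safety data are not formally tested. These safeguards are real, but listings give no incidence by arm, and the event tables depend on an investigator reporting an event.

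**Conclusion.** The point holds as a gap in the record-selection rules. If the continuous rules feed the by-visit glucose grade table, as their stated scope implies, a Grade 3 or higher value can be displaced by a lower same-day retest or by a lower reading nearer the target day. Separately, the SAP does not say whether grading comes before or after selection, or which records supply the Grade 3 or higher incidence table.

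The size cannot be estimated from the documents. It depends on how often such values occur, how often they are repeated, and laboratory windows that are not in the SAP. The firm figure is the weight of one patient: 2.6 percentage points on TEPEZZA, 5.3 on placebo. The primary efficacy analysis, the type I error and the sample size are untouched. The point is modest, but cheap to settle and best settled before unmasking.

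**What to change.** Amend SAP 5.4.3 and 10.2 as follows.

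1. Limit the nearest-day, averaging and retest rules to descriptive summaries of values and change from Baseline.
2. Assign CTCAE grades and low/normal/high categories to every valid post-baseline record before any selection. Use the worst value in each window for the shift tables, and state the direction of worst where a test can be abnormal both ways.
3. Count Grade 3 or higher fasting glucose over all valid fasting post-baseline records in the treatment period, including unscheduled readings and the first of a retested pair.
4. Exclude a first value only if the laboratory declares it invalid.

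The cost is SAP wording and one derived worst-value flag. There are two small downsides. The reported incidence may be slightly higher. Means and graded tables may also rest on different records, which a table footnote should state.
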